- Percentage of participants maintaining type 2 diabetes remission at 18 months, defined as HbA1c <6.5% after 12 months post-intervention and at least 9 months without antidiabetic medication.
- Percentage of participants maintaining type 2 diabetes remission at 18 months, defined as fasting venous plasma glucose <126 mg/dL after 12 months post-intervention and at least 9 months without antidiabetic medication.
- Change in dietary patterns at 6 and 18 months, assessed using a validated 24-hour dietary recall questionnaire, to evaluate adherence to the nutritional component of the intervention.
- Change in physical activity level at 6 and 18 months, measured using the International Physical Activity Questionnaire (IPAQ).
- Change in health-related quality of life at 6 and 18 months, assessed using validated instruments such as the SF-36 or EQ-5D questionnaires.
- Change in cardiovascular risk factors at 6 and 18 months, including blood pressure, total cholesterol, HDL cholesterol, LDL cholesterol, Apo B100, triglycerides, and presence and size of carotid atherosclerotic plaques.
- Change in metabolic indicators at 6 and 18 months, including weight, Body Mass Index (BMI), waist

circumference, insulin resistance (HOMA-IR index), pancreatic beta-cell function (HOMA-B index), and fasting insulin.

Study Population: The study population consists of patients with type 2 diabetes (T2DM) assigned to the Primary Care centers of Barceloneta and Larrard at Parc Sanitari Pere Virgili, Barcelona.

Phase* or Stage: N/A.

[figure not shown]
Description of Sites/Facilities Enrolling Participants: Multicenter Study Sites
Barceloneta Primary Care Center, Parc Sanitari Pere Virgili, Barcelona, Spain
Larrard Primary Care Center, Parc Sanitari Pere Virgili, Barcelona, Spain

Description of Study Intervention/Experimental Manipulation: The program consists of biweekly in-person and telephone visits, focused on implementing a personalized dietary plan with carbohydrate restriction, based on the American Diabetes Association recommendations; moderate and accessible physical activity; circadian rhythm regularization; and psychological counseling and support.

Study Duration: 3 years.

Participant Duration: 18 months (6 months of intervention and follow-up assessments one year after completion of the intervention).

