2.3 RISK/BENEFIT ASSESSMENT

2.3.1 KNOWN POTENTIAL RISKS

Due to the nature of the study, which focuses on dietary and lifestyle changes in patients, the risks associated with this type of intervention are very low. However, potential risks may include:

- **Immediate risks:** Dietary changes and increased physical activity may trigger mild adverse effects. For example, participants may experience episodes of constipation, fatigue, or minor muscle discomfort related to increased physical activity.
- **Long-term risks:** In individuals with type 2 diabetes (T2DM) who discontinue pharmacological treatment due to metabolic improvement, there is a risk of hyperglycemia if the long term adherence to lifestyle programm fails. This risk will be minimized through close medical monitoring during the study.

No alternative interventions were proposed due to the low risk of adverse effects and to avoid interfering with the intervention as defined in the protocol.

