4 STUDY DESIGN

4.1 OVERALL DESIGN

The study is designed as an open-label, randomized clinical trial. The strategy includes Group A – Intervention, which will undergo the CREDOenAP program, and a parallel control group, Group B – Control, which will receive standard T2DM care from a primary care team (family physicians

and nurses) without any intervention from the research team, except for data collection at baseline and at the end of each study phase.

The study has been designed to evaluate the effectiveness of a lifestyle-focused intervention (CREDOenAP) on T2DM reversal in primary care patients. It is a multicenter study involving two primary care centers in Barcelona (CAP Larrad and CAP Barceloneta).

The main hypothesis is that the proposed intervention, based on a structured and culturally adapted program, is effective in achieving biochemical and functional remission of T2DM. The study design corresponds to a randomized clinical trial aimed at establishing the initial efficacy of the intervention under real-world clinical practice conditions.

Each center will recruit participants who will be randomly assigned in a 1:1 ratio to each study arm. Recruitment is planned as follows:

- Center 1 (CAP Barceloneta): Group A – Intervention (20 participants) and Group B – Control (20 participants).
- Center 2 (CAP Larrad): Group A – Intervention (40 participants) and Group B – Control (40 participants).

Group A – Intervention, comprising a total of 60 participants (20 from Center 1 and 40 from Center 2), will receive standard care plus the CREDOenAP intervention.

Group B – Control, comprising a total of 60 participants (20 from Center 1 and 40 from Center 2), will receive standard care alone.

Both Group A – Intervention and Group B – Control will include patients meeting the inclusion and exclusion criteria, with assignment conducted via stratified randomization. Potential participants will be validated by a healthcare professional not involved in the intervention to exclude false positives due to registration errors.

For stratification, performed through statistical programming, relevant characteristics that may act as potential confounding variables will be considered. In this study, stratification will be based on:

- Healthcare center (Center 1: CAP Barceloneta / Center 2: CAP Larrad)
- Sex (Male / Female)
- Age (18–50 years / \geq 50 years)
- Years since T2DM diagnosis (<5 years / \geq 5 years)

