6.5.1 RESCUE THERAPY

In the event of a significant glycemic decompensation in any participant (HbA1c > 9% or presence of symptoms), the study team may initiate pharmacological treatment based on clinical judgment or refer the participant to their usual physician for further evaluation. The date, type, and dose of any medication initiated will be recorded.

7 STUDY INTERVENTION/EXPERIMENTAL MANIPULATION DISCONTINUATION AND PARTICIPANT DISCONTINUATION/WITHDRAWAL

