Potential participants will receive an invitation to take part in the study during their last medical consultation (in person or by telephone) by their physician, nurse, or the principal investigator. They will then be scheduled for a screening visit with a member of the research team, following completion of the screening blood test. Patients will be informed of the necessary requirements for the laboratory tests (fasting status and first morning urine sample) as well as the location where they will be carried out (extraction and laboratory areas of each primary care center).

Screening and Study Inclusion Visit

During this visit, eligibility criteria will be assessed to determine whether patients meet the study selection requirements. Participants who fulfill the criteria will receive a detailed explanation of the study objectives and the implications of participation. They will be provided with the study information sheet and, if they agree to participate, will sign an informed consent form for data collection throughout the study. If consent is obtained, a physical examination (anthropometric measurements) will be performed, sociodemographic variables will be recorded, and participants will complete the questionnaires assessing quality of life, physical activity, nutritional status, and lifestyle habits (including substance use). Additionally, appointments will be scheduled for all participants to undergo the imaging test (Carotid ultrasonography).

Laboratory Tests

Blood and urine analyses will be performed at three different time points during the study: at baseline, at the end of the intervention, and 12 months after completion of the intervention. These analyses do not involve any additional procedures, as they are part of the routine clinical practice for monitoring and follow-up of all patients with type 2 diabetes mellitus (T2DM) in primary care. No requests, extractions, or analyses will be conducted outside of standard clinical care. The laboratory tests will include: Complete blood count, HbA1c, Creatinine, Glomerular filtration rate, GOT (AST), GPT (ALT), GGT, Ionogram, Lipid profile (Total cholesterol, HDL, LDL,

Triglycerides, Apo B100), Fasting insulin, Anti-GAD antibodies (only at baseline), Urine: sediment and albumin/creatinine ratio.

Imaging Diagnosis: Carotid ultrasonography

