9.4.2 ANALYSIS OF THE PRIMARY ENDPOINT(S)

The primary endpoint is the change in glycated hemoglobin (HbA1c, %) from baseline to 6 months. HbA1c is measured as a continuous variable on an interval scale. The endpoint will be calculated as the absolute difference between baseline HbA1c and the value obtained at 6 months.

The primary analysis will be performed using analysis of covariance (ANCOVA) with treatment group (intervention vs. control) as the fixed factor, and baseline HbA1c as a covariate to improve precision. Additional prespecified covariates will include age, sex, study site, and randomization block, based on their potential clinical relevance and to ensure adjustment for any residual imbalance despite randomization. A secondary, confirmatory analysis will be conducted using a

mixed-effects model for repeated measures (MMRM), which includes all available timepoints (baseline, 3 months, and 6 months). This model accounts for within-subject correlation by specifying an unstructured covariance matrix.

Results will be presented as adjusted mean differences between groups with 95% confidence intervals and corresponding two-sided p-values. Least-squares means (LSMEANS) will be used to report group means adjusted for covariates.

The Intention-to-Treat (ITT) population will be the primary analytic set, including all randomized participants according to their allocated group. A Per-Protocol (PP) population, defined as participants with at least 70% adherence to the intervention, will be analyzed as a sensitivity approach.

Handling of Missing Data; for ANCOVA, missing data at 6 months will be addressed using multiple imputation under the missing-at-random (MAR) assumption. In MMRM, missing data are implicitly handled under MAR. Additional sensitivity analyses will explore the robustness of results to different missing-data mechanisms.

For ANCOVA, residuals will be checked for normality and homoscedasticity. If these assumptions are substantially violated, transformations or nonparametric methods will be considered. For MMRM, model fit will be evaluated and alternative covariance structures tested.

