9.4.3 ANALYSIS OF THE SECONDARY ENDPOINT(S)

The secondary endpoint is diabetes remission at 18 months, defined as achieving HbA1c <6.5% without glucose-lowering medications. It will be analyzed using a generalized linear mixed-effects model (GLMM) with a logit link, including treatment group, time, and group \times time interaction as fixed effects, and a random intercept for participants to account for repeated measurements. Prespecified covariates include baseline HbA1c, age, sex, site, and randomization block. Results will be reported as adjusted odds ratios with 95% confidence intervals and two-sided p-values.

The analysis will follow the Intention-to-Treat (ITT) principle; a Per-Protocol (PP) analysis (adherence $\geq 70\%$) will be performed as sensitivity. Missing data will be handled under the missing-at-random assumption, with multiple imputation applied if necessary. Trajectories of remission probabilities over time will also be presented.

Others secondary endpoints include:

- Change in body weight (kg) from baseline to 6 months (continuous, interval scale).
- Change in blood pressure (systolic and diastolic, mmHg) from baseline to 6 months (continuous, interval scale).
- Change in lipid profile (total cholesterol, LDL-C, HDL-C, triglycerides, mg/dL) from baseline to 6 months (continuous, interval scale).
- Change in circadian rhythm regularity (measured via validated questionnaire scores; ordinal/interval scale).

- Change in health-related quality of life (measured via validated scale, e.g., SF-12 or equivalent; interval scale).
- Intervention adherence (measured as percentage of scheduled sessions completed; continuous, but categorized as adherent $\geq 70\%$ vs. non-adherent for analysis).

The analysis models for continuous outcomes (e.g., weight, blood pressure, lipid levels, quality of life scores) will be analyzed using ANCOVA with treatment group as a fixed factor and baseline values as covariates. Repeated measures across timepoints (baseline, 3 months, 6 months) will be analyzed with MMRM to account for within-participant correlations.

For binary/categorical outcomes (e.g., adherence $\geq 70\%$, achievement of HbA1c $< 6.5\%$) will be analyzed using logistic regression, adjusted for prespecified covariates.

For ordinal outcomes (e.g., circadian rhythm scores if treated as ordinal), ordinal logistic regression will be considered.

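### Glycaemic worsening at 18 months, the long-term risk the protocol itself names, has no planned between-arm comparison, because the 18-month HbA1c is used only as remission yes/no

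*Protocol*

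**What the plan says.** **The named risk.** Protocol section 2.3.1 says that, in people who stop drug treatment after metabolic improvement, "there is a risk of hyperglycemia if the long term adherence to lifestyle programm fails". It is listed as the long-term risk, so it falls mainly in the year after the programme.

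**The measurement.** Section 8.1 schedules laboratory tests, HbA1c included, "at baseline, at the end of the intervention, and 12 months after completion of the intervention". Section 4.1 leaves controls to usual care "except for data collection at baseline and at the end of each study phase", so they are measured at the same points.

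**The analysis of HbA1c.**
- To month 6 it is continuous. Section 9.4.2 states: "The primary endpoint is the change in glycated hemoglobin (HbA1c, %) from baseline to 6 months". The supporting mixed model is one "which includes all available timepoints (baseline, 3 months, and 6 months").
- At month 18 it is binary. Section 9.4.3 states: "The secondary endpoint is diabetes remission at 18 months, defined as achieving HbA1c <6.5% without glucose-lowering medications". The result is an adjusted odds ratio with remission-probability trajectories.
- Fasting glucose at month 18 is also cut, "defined as fasting venous plasma glucose <126 mg/dL after 12 months post-intervention and at least 9 months without antidiabetic medication" (section 1.1).
- The metabolic indicators followed to 18 months (sections 1.1 and 3) are body size, HOMA-IR, HOMA-B and insulin. HbA1c is not among them.

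**Safety.** Section 9.4.4 reads N/A. Section 6.5.1 says of rescue treatment: "The date, type, and dose of any medication initiated will be recorded".

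**The concern.** The 18-month result will carry the claim of durable benefit. The same blood sample could also show whether participants who did not stay in remission ended up worse than under usual care, which is the long-term risk the protocol describes. The chosen scale removes that information. Below 6.5% without drugs is one category and everything else is the other, so someone now well above baseline is indistinguishable from someone who has not moved.

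The baseline position makes this matter more than the usual loss from dichotomising. Section 5.1 requires a most recent HbA1c above 6.5%, so participants start in the unfavourable category and cannot move to a worse one. At stake is the benefit-risk reading. An identical remission difference would be reported whether the remaining intervention participants are better than, equal to or worse than controls.

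**Working it through.** **Step 1. The planning figures.** Section 9.2 gives control remission of 0 to 5%, intervention remission of at least 25%, two-sided alpha 0.05, beta below 0.2, at least 52 per arm, and 60 recruited with 15% loss (60 × 0.85 = 51). For 5% versus 25%, a normal-approximation calculation without continuity correction gives 82.5% power at 52 per arm and 81.7% at 51. This point does not dispute the sample size.

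**Step 2. Room for an adverse result.** If control remission is 0%, the difference cannot be negative. If it is 5% (3 of 60), the worst possible intervention result is 0 of 60, a difference of −5 points. With three remitters in 120 people, the chance that all three fall in the control arm is (60 × 59 × 58)/(120 × 119 × 118) = 0.122. The two-sided Fisher p is therefore 2 × 0.122 = 0.24. The most adverse outcome available would not reach significance.

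**Step 3. What the binary scale hides (illustration).** The protocol gives no 18-month remission rates, HbA1c means or SD. The assumptions are:
- the 6-month planning rates of 25% and 5% are carried to month 18;
- remitters average 6.2% and control non-remitters 7.8%;
- the SD among non-remitters is 1.0;
- intervention non-remitters average 7.8 + *w*;
- there are 51 per arm.

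Mean difference (intervention minus control) = [0.25 × 6.2 + 0.75 × (7.8 + *w*)] − [0.05 × 6.2 + 0.95 × 7.8] = −0.32 + 0.75*w*.

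Expected number above 9% (the HbA1c figure in section 6.5.1) = 51 × share of non-remitters × P(Normal > 9).

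| *w* | Remission | Mean HbA1c difference | Above 9%, intervention | Above 9%, control |
|---|---|---|---|---|
| 0 | 25% vs 5% | −0.32 | 4.4 | 5.6 |
| 0.5 | 25% vs 5% | +0.06 | 9.3 | 5.6 |
| 1.0 | 25% vs 5% | +0.43 | 16.1 | 5.6 |
| 1.5 | 25% vs 5% | +0.81 | 23.6 | 5.6 |

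The sign changes at *w* = 0.32/0.75 = 0.43. Not every non-remitter needs to worsen: an average of 0.5 arises if one third worsen by 1.5 points (1.5/3 = 0.5).

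Other assumed values (remitters 6.1%, control non-remitters 7.5%, SD 1.1) give the same pattern. The mean difference is −0.28 + 0.75*w*: 7.15 versus 7.43 at *w* = 0, and 7.90 versus 7.43 at *w* = 1. The shares above 9% are about 6% versus 8% and 24% versus 8%.

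**Step 4. Would a continuous comparison be informative?** The difference detectable with 80% power is (1.960 + 0.842) × SD × √(2/51), again with assumed SDs.

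| SD | Detectable difference | Power for 1.0 point | Power for 0.5 point |
|---|---|---|---|
| 1.0 | 0.55 | 99.9% | 71% |
| 1.25 | 0.69 | 98.1% | 52% |
| 1.5 | 0.83 | 92.0% | 39% |

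A mean difference of one point would very probably be seen. Half a point might be missed, so the estimate and its interval should be read, not just the p-value.

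**The case against.** The best reply is that worsening is not invisible in this trial, and much of that reply stands.

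- **Adverse events.** Section 8.3.4 has deterioration of type 2 diabetes recorded as an adverse event, and section 1.3 marks event recording at 18 months. A reader might infer that a worsening is reported as no event. That is true only of the remission analysis. However, no between-arm analysis of events is given, and the fortnightly recording follows the intervention visits, so ascertainment is uneven between arms.
- **Hyperglycaemia episodes.** Section 8.1 introduces these variables as assessed also one year after completion. The definition, though, covers symptomatic values above 350 mg/dl during the intervention, and the table marks none at 18 months.
- **Drug use.** A reader might infer that drug restarts leave no trace in the endpoints. Section 3 lists change in Defined Daily Dose at 6 and 18 months as exploratory, so they would leave one. It measures amount, not who started or restarted antidiabetic drugs, and it does not measure glycaemia.
- **HOMA-IR.** Its formula contains fasting glucose, so glycaemia enters a continuous 18-month variable, but multiplied by insulin.
- **Two-sided test.** It is tempting to say the 18-month analysis can only show benefit. The test is two-sided and may be null or adverse. What holds is that, at the planning rates, its adverse range is very small.
- **HbA1c can hide harm too.** A relapse treated with drugs may show an acceptable value at month 18. HbA1c is therefore not a sufficient measure of this harm on its own.
- **Constructed figures.** The scenarios in step 3 were built with equal remission, so the binary result cannot differ between them. The named risk also concerns only those who stopped drugs and then lost adherence, so a one-point average shift across all non-remitters is a severe case.

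Remission at 18 months is a legitimate secondary objective, and a binary analysis answers it. Nor can the matter simply be left to a statistical analysis plan, because the protocol itself sets the 6-month limit for continuous HbA1c, the binary form at 18 months and N/A for safety.

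**Conclusion.** The point holds as a gap between the stated risk and the stated analysis. Followed as written, the protocol gives no between-arm comparison of glycaemia at 18 months that could show worsening among non-remitters, although the measurement is scheduled in both arms. The loss is near complete for this purpose: at the planning rates the remission difference can fall no lower than −5 points. In the illustration the mean HbA1c difference moves by 1.13 points (−0.32 to +0.81) with no change in the remission result.

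The size rests on assumed HbA1c means and SD and on 6-month rates applied to month 18. It shows what could go unseen and does not predict what will happen. Nothing in the protocol shows that the intervention worsens glycaemia, and this point does not claim so. The change should be made because it is cheap and bears directly on the durability and benefit-risk conclusions.

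**What to change.** **Section 9.4.3.** Add a baseline-adjusted between-arm comparison of continuous HbA1c at 18 months in all randomised participants, for example by extending the HbA1c mixed model of 9.4.2 to month 18. Report the adjusted difference with its 95% confidence interval.

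**Section 9.4.4.** Replace N/A with a table by arm at 6 and 18 months showing:
- the number with HbA1c above their own baseline;
- the number above the protocol's own 9% figure, as a descriptive cut only;
- the number who started or restarted antidiabetic drugs.

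Read these with the planned Defined Daily Dose endpoint, because a drug restart can lower the 18-month HbA1c. State that the 18-month remission result is always reported beside these figures.

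**Cost.** One model and one table from data already scheduled, with no new visit, test or staff. The durability claim may look less favourable. No treatment threshold, rescue rule or other clinical rule is altered.

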In the United Kingdom, within primary care settings, the DiRECT series of studies (*Lean et al., 2018*), were conducted, focusing on weight loss through a low-calorie diet. These studies were designed to evaluate whether effective weight control could induce sustained remission of type 2

diabetes (T2DM), restricting the participation to individuals aged 20–65 years who had been diagnosed with T2DM within the past 6 years, had a body-mass index of 27–45 kg/m², and were not receiving insulin. In the DiRECT study (149 participants per group), conducted across 49 primary care practices in Scotland and England, 24% of participants in the intervention group achieved a weight loss of 15 kg or more at 12 months, compared to none in the control group (P < 0.0001). T2DM remission was achieved in 46% of participants in the intervention group and 4% in the control group (odds ratio 19.7; 95% CI 7.8–49.8; P < 0.0001). A clear correlation was observed between remission rates and weight loss. The DiRECT program maintained remission at 24 months in more than one-third of participants with T2DM (*Lean et al., 2019*) with sustained remission associated with maintenance of the achieved weight loss.

This weight-loss-focused approach with dietary caloric restriction has been applied in other studies, achieving diabetes remission rates ranging from 47.2% (*Yang et al., 2023*) to over 60% of participants (*Taheri et al., 2020*), using various caloric restriction strategies and more restrictive inclusion criteria.

Another research group in the United Kingdom has published several articles in the form of clinical audits, reporting beneficial effects of diabetes remission through carbohydrate restriction. These effects include improvements in arterial hypertension, renal function, dyslipidemia, weight loss, and other metabolic parameters. (*Unwin et al., 2020, 2021, 2023; D. J. Unwin et al., 2019*).

In a series of publications, a telemedicine intervention group in the United States demonstrated several metabolic benefits of type 2 diabetes (T2DM) reversal through nutritional ketosis, with or without weight loss and without intentional caloric restriction. (*Athinarayanan et al., 2019; Bhanpuri et al., 2018; Hallberg et al., 2018; McKenzie et al., 2017*).

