9.2 SAMPLE SIZE DETERMINATION

Based on the primary variable of the intervention, the percentage of T2DM remission, the required sample size has been calculated to observe statistically significant differences. This variable will be coded dichotomously. A total of 120 volunteers (60 per arm) will be recruited for the study. Accepting an alpha risk of 0.05 (5%) and a beta risk of less than 0.2 in a two-sided test, at least 52 subjects in the control group and 52 subjects in the intervention group would be required to detect as statistically significant a 20% difference between two proportions (primary endpoint: T2DM remission). For the control group, the expected remission rate ranges from 0 to 5%, whereas in the intervention group, it is expected to be at least 25%. The remission rates have been benchmarked against previous studies (Lean et al., n.d.). An estimated loss to follow-up rate of 15% has been considered.

Given the estimated 15% loss to follow-up, the sample size has been increased to 60 participants instead of 52. This ensures that the statistical power of the analysis will be preserved.

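### Section 9.4.3 reports 18-month remission as a subject-specific odds ratio from a random-intercept logit model, although the endpoint is the percentage in remission by arm; under plausible persistence this odds ratio can far exceed the between-arm one

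*Protocol*

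**What the plan says.** Section 9.4.3 analyses 18-month remission with a generalised linear mixed model with a logit link. It has fixed effects for group, time and their interaction, "and a random intercept for participants to account for repeated measurements", with baseline HbA1c, age, sex, site and randomisation block as covariates. The effect measure is fixed: "Results will be reported as adjusted odds ratios with 95% confidence intervals and two-sided p-values". The section does not say whether these odds ratios are conditional on the random intercept or averaged over it.

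The section also plans to show remission probabilities over time and, for binary endpoints when applicable, absolute risk differences and numbers needed to treat. Other binary outcomes, with reaching HbA1c below 6.5% as an example, "will be analyzed using logistic regression, adjusted for prespecified covariates".

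The endpoint in sections 1.1 and 3 is a percentage of participants, and the primary hypothesis in section 9.1 compares the percentage in remission between arms. Section 8.1 records remission status at baseline, at the end of the intervention and 12 months later.

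**The concern.** In a logit model with a participant random intercept, the exponentiated group coefficient compares two people who have the same latent propensity to remit. It does not compare the two arms as randomised. The two coincide only when the intercept variance is zero. As that variance grows, the conditional odds ratio moves further from 1 for the same pair of arm percentages. This is a property of the model: it remains at any sample size and does not come from empty cells.

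The variance may well be large here. Section 5.1 requires HbA1c above 6.5% at entry, so nobody is expected to be in remission at baseline and only months 6 and 18 carry information. Remission is also a state that tends to last. Section 2.2 reports that the benchmark programme reached 46% at 12 months and "maintained remission at 24 months in more than one-third of participants with T2DM".

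What is at stake is the interpretation of the prespecified estimate for durability. Readers will naturally take it as the between-arm effect, or set it beside ordinary logistic odds ratios from the same section, and it is neither.

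**Working it through.** **Plan's own figures.** The protocol states no 18-month odds ratio, intercept variance or persistence, so there is nothing of that kind to reproduce. Section 9.2 gives the remission rates behind the design: for controls "the expected remission rate ranges from 0 to 5" per cent, and "in the intervention group, it is expected to be at least 25" per cent. For two-sided 5% significance and power above 80% it states a requirement of 52 per arm. The pooled normal formula gives

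n = [1.96·√(2·0.15·0.85) + 0.842·√(0.05·0.95 + 0.25·0.75)]² / 0.20² = 48.8, i.e. 49 per arm,

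and 52 per arm gives 82.5% power. That agrees with the stated power, and the sample size is not at issue. I take 25% and 5% from it as the 6-month rates.

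**Assumptions not in the documents.** At 18 months, 20% in the programme arm and 5% in controls. Persistence q = P(remission at 18 | remission at 6), varied from 0.4 to 0.7. No covariates.

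**Between-arm odds ratios.**
- Month 6: (0.25/0.75)/(0.05/0.95) = 6.33
- Month 18: (0.20/0.80)/(0.05/0.95) = 4.75

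**Mixed-model odds ratios.** The model is logit P(y=1) = b0 + b1·g + b2·t + b3·g·t + τ·u, with u standard normal and integrated on a fine grid. It was fitted by maximum likelihood to the exact joint probabilities of the two visits in each arm. For q = 0.6 these are, in the order both visits, month 6 only, month 18 only, neither:
- Programme: 0.15, 0.10, 0.05, 0.70
- Control: 0.03, 0.02, 0.02, 0.93

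The conditional odds ratio is exp(b1) at month 6 and exp(b1+b3) at month 18. With equal persistence in both arms:

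| q | intercept SD | OR month 6 | OR month 18 | month 18 ÷ 4.75 |
|---|---|---|---|---|
| 0.4 | 1.9 | 14.0 | 9.1 | 1.9 |
| 0.5 | 2.8 | 26 | 15.3 | 3.2 |
| 0.6 | 4.0 | 75 | 36.4 | 7.7 |
| 0.7 | 6.4 | 647 | 213 | 45 |

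The fitted arm percentages reproduce the inputs to within 0.2 points, so the gap is not misfit.

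**Sensitivity.**
- Control persistence 0.3, programme persistence 0.4, 0.5, 0.6, 0.7: the month-18 odds ratio is about 8, 11, 18 and 38, i.e. 1.7, 2.4, 3.8 and 7.9 times 4.75.
- Rates stable at 25% vs 5% (between-arm 6.33), intercept SD set to match programme-arm persistence: 12.6 (2.0 times) at 0.5, 22.7 (3.6 times) at 0.6, 62 (9.8 times) at 0.7.
- Same stable rates with intercept SD 1.0, which implies persistence of only 0.36: 7.8 (1.2 times).

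**The case against.** A conditional odds ratio is a valid and common effect measure, and in this model it equals 1 at a visit exactly when the between-arm odds ratio does. The test is therefore not misdirected, and the question is one of interpretation. That stands.

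A reader might infer that a fading effect would be reported as a growing one: about 6 at month 6 from logistic regression, then 36 at month 18 from the mixed model. The documents do not set up that comparison. The model has a group-by-time term, so it supplies its own 6-month odds ratio, and in the table the effect fades in every row. The logistic sentence is not assigned to 6-month remission either. It covers other binary outcomes, and its HbA1c example lacks the medication-free condition. The primary analysis in section 9.4.2 is a mean HbA1c difference, which no odds ratio can be set against.

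A reader might also infer that the durability result as a whole is overstated tenfold. That goes too far. Probabilities over time are promised, with risk differences and numbers needed to treat when applicable, so the odds ratio would not stand alone. The benchmark's fall from 46% to more than one third is a ratio of two aggregate rates (at least about 0.33/0.46 = 0.72), not within-person persistence. Baseline HbA1c as a covariate may lower the intercept variance.

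What remains is that the protocol itself fixes the model and the odds ratio as the result carrying the confidence interval and p-value. It does not say that the probabilities are averaged over the random intercept; evaluated at an intercept of zero, they would not be arm percentages. The risk differences are conditional in wording and tied to no method for this model.

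**Conclusion.** The point holds in limited form. The prespecified effect measure for 18-month remission does not match an endpoint and hypothesis stated as percentages by arm. Under the assumptions above it is about 2 to 45 times the between-arm odds ratio of 4.75 for persistence 0.4 to 0.7 equal in both arms, and about 1.7 to 8 times if control persistence is 0.3. With a small intercept variance the gap nearly disappears. Since the protocol gives neither persistence nor variance, these figures show what can happen and do not predict the trial's result. The odds ratio should not be read as a between-arm effect or placed beside ordinary logistic odds ratios. Comparison with month 6 remains possible within the model. This is a cheap improvement to the reported measure; it does not invalidate the analysis.

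**What to change.** In section 9.4.3, name a population-averaged contrast as the headline result for remission at both 6 and 18 months: standardised risks by arm and their difference, with 95% CI. Obtain it either by integrating the fitted mixed model over the random intercept, or from logistic regression at each visit or GEE with robust standard errors on the multiply imputed data. Compute the planned probability trajectories the same way. If the mixed-model odds ratio is still shown, label it as conditional on the participant intercept and give months 6 and 18 together.

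The cost is a sentence or two of text and slightly more analysis work. Plain GEE is not valid under missing at random by itself, so that route needs multiple imputation, which the section already allows for.
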